1 INTRODUCTION

This observational clinical study is intended to collect real world evidence (RWE) on the safety and efficacy of transcatheter device closure of patent ductus arteriosus (PDA) using the Amplatzer Piccolo Occluder in premature infants with a weight of less than 2 kg at the time of device implant. This clinical study is sponsored by Abbott.

All US clinical sites/physicians enrolling in the Congenital Cardiac Interventional Study Consortium (CCISC) are eligible to participate in the study following satisfactory completion of qualification requirements.

1.1 Study Objective

The objective of this study is to demonstrate the continued safety and efficacy in a real-world setting of transcatheter device closure of the PDA in premature infants less than 2kg in weight at the time of device implant performed at the CCISC participating centers.

1.2 Study Design

This is a multi-center, single arm, non-randomized, observational study designed to help assure continued safety and effectiveness of FDA approved Amplatzer Piccolo Occluder device for PDA closure in premature infants less than 2 kg at the time of device implant. The study will be conducted at all the CCISC participating sites.

Subjects will have transcatheter PDA closure using the Amplatzer Piccolo Occluder device as part of standard clinical practice under fluoroscopy with or without additional echocardiographic image guidance. The study involves collecting and reporting of data for the ASO II AS PDA closure procedures into the CCISC PDA Module Database. The PDA module encompasses pre-procedure, procedure, 48-hoours, 1-month and 6-months post-procedure follow-up data entry. It also encompasses an adverse event reporting system. Data entry is expected for all attempted PDA closure procedures in which the Amplatzer Piccolo Occluder device is attempted in premature infants weighing < 2 kg at the time of the procedure. It includes pre-procedural and postprocedural echocardiographic information as well as data from procedural echo guidance if utilized. Follow-up will be for a period of six months +/- 30 days after the procedure.

2. STUDYENDPOINTS

Initial data collection will be limited to 500 subjects. Additional data collection beyond the initial cohort of 500 subjects may be done on a voluntary basis by participating sites/physicians.

2.1 Primary Endpoint(s)

Safety Endpoint: Composite rate of major device- or procedure-related adverse events (AE) of interest through 6 months' post-implantation procedure. AEs of interest are broadly categorized as:

- a. Vascular access complications
- **b.** Valvular Injury
- **c.** Device embolization
- d. Pulmonary or aortic vessel stenosis

Access vessel complications include femoral arterial or femoral/jugular venous complications noted during the procedure, immediately after the procedure or delayed (>24 hours). They range from bleeding from access sites, arterial or venous thrombosis with or without the need for treatment to loss of limb secondary to arterial occlusion.

Valvular injury includes damage to the tricuspid valve or other cardiac valve resulting in immediate post-procedural valvular dysfunction.

Device embolization includes malposition of the device either during or after the procedure or delayed (>24 hours). The outcome of device embolization ranges from observation, transcatheter retrieval at time of procedure or at a separate time, surgical retrieval, other end organ damage, tomortality.

Adjacent vessel stenosis includes a narrowing of the aorta or the left pulmonary artery directly as a consequence of device implantation for PDA closure. Vessel stenosis could happen either during or after the procedure or delayed (>24 hours). The outcome of vessel stenosis ranges from no intervention needed to repeated transcatheter and surgical therapies.

For details of each AEs and definitions, refer to **Appendix A**.

Effectiveness Endpoint: The effectiveness endpoint is the rate of effective closure of the PDA using a transcatheter device within six months post procedure. If more than one attempt is required, or multiple devices are required during the same procedure, it is still considered effective if there is Grade 0 or Grade 1 shunt, as defined below, at follow-up (within six months) by transthoracic echocardiography (TTE) or if a second procedure is not required following the initial attempt. If there is device embolization, adjacent vessel stenosis that required retrieval of the device and replacement during the same procedure with less than Grade 1 shunt during follow-up, it is still considered effective. Conversely, if an AE is noted after the procedure that requires a second procedure for treatment that results in greater than Grade 1 shunt, then the procedure is considered not effective, even if the initial attempt was effective.

PDA shunt definition:

Grade 0—none;

Grade 1—trivial (narrow jet adjacent to the device via the PDA). Note: the presence of flow via existing or newly formed aortopulmonary collaterals should not be considered as representing a shunt via the PDA. (See references in **Appendix B** by Skinner and Acherman)

Grade 2—mild (broader jet filling proximal left pulmonary artery branch and extending to main pulmonaryartery);

Grade 3/4—moderate to severe (wide jet filling the main pulmonary artery and extending to pulmonary valve or distal pulmonary artery branches, which also may be accompanied with the presence of flow reversal in the abdominal aortic Doppler pattern during diastole)

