5.3 Specific Adverse Events

The adverse event form includes specific risks associated with transcatheter device closures that needs to be followed. They include:

- a. Access complications: Include site, timing and type of complication, and outcome
- b. Valvular injury: Include site, timing and type of complication, and outcome
- c. Device embolization: Include timing of embolization, embolization site and outcome
- d. Vessel stenosis: Include timing of vessel stenosis, site of vessel stenosis and outcome

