No intervention was required Intervention performed during the same catheterization Intervention performed within 24 hours Intervention performed > 24 hours Re-intervention on the left pulmonary artery is unlikely Re-intervention on the left pulmonary artery is likely *Type of intervention for the left pulmonary artery stenosis*: Retrieval of device with no further intervention Retrieval of device with repositioning of the same device Retrieval of device with use of a different device Balloon angioplasty of the left pulmonary artery stenosis Surgical repair

Descending aorta stenosis:

No intervention was required Intervention performed during the same catheterization Intervention performed within 24 hours Intervention performed > 24 hours Re-intervention on the aorta is unlikely Re-intervention on the aorta is likely

Type of intervention for the descending aorta stenosis:

Retrieval of device with no further intervention Retrieval of device with repositioning of the same device Retrieval of device with use of a different device Balloon angioplasty of the descending aorta stenosis Stent implantation for descending aorta stenosis Surgical repair

Valve	e Injury:
	Noted during the procedure (In the cath lab): Yes No
	Noted after the procedure (In recovery): Yes 📃 No 🔜
	Delayed finding (>24 hours later): Yes No
Injure	ed Valve:
	Tricuspid valve
	Pulmonary valve
	Mitral valve
	Aortic valve
Degre	ee of regurgitation:
	Mild
	Moderate
	Severe
Mech	anism of regurgitation:
	Avulsion of chordae
	Avulsion of chordae Central non-coaptation of the valve Valve leaflet injury Injury to valve appulus
	Valve leaflet injury
	Injury to valve annulus
Outco	ome:
	Observation only
	Medical therapy
	Surgical intervention

Other complications: Bleeding into: Pericardium Pleura Peritoneum Retroperitoneum External hemorrhage Vessel perforation Cardiac arrest Arrhythmias including AV heart blocks Stroke Death Infection including suspected endocarditis and sepsis Post PDA ligation syndrome

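### Section 2.1 limits valvular injury to immediate dysfunction, while Section 7.1 with Appendix A sets no onset limit, so a late major valve injury could be classified either way in the primary safety endpoint

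*Protocol*

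**What the plan says.** Section 2.1 defines the primary safety endpoint as the "Composite rate of major device- or procedure-related adverse events (AE) of interest through 6 months' post-implantation procedure" and names four broad categories, each with a short description.

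- Access complications are those "noted during the procedure, immediately after the procedure or delayed (>24 hours").
- "Device embolization includes malposition of the device either during or after the procedure or delayed (>24 hours").
- "Vessel stenosis could happen either during or after the procedure or delayed (>24 hours").
- Valvular injury is said to include damage to the tricuspid or another valve "resulting in immediate post-procedural valvular dysfunction".

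Only the last has no delayed category. Section 2.1 refers the reader to Appendix A for definitions. Appendix A does not define valvular injury, and its examples of major and minor complications do not mention valves.

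The data collection is wider than that description. Section 5.3 asks for "Valvular injury: Include site, timing and type of complication, and outcome". The valve block of the Appendix D form has the entry "Delayed finding (>24 hours later): Yes No". Section 4.4 and Appendix E schedule echocardiography, including pulmonic and tricuspid regurgitation, within 48 hours, at one month and at six months.

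Section 7.1 states the endpoint for analysis as the rate of major adverse events up to six months after an attempted implant, as defined in Appendix A. Appendix A classes a related event as major by its consequence: death, threat to life, persistent or significant disability, or major open surgery. It sets no limit on onset.

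**The concern.** Three parallel descriptions admit delayed events and the fourth says *immediate*. A reader could reasonably take that limit as deliberate, yet the protocol gives no reason for it, and Section 7.1 and Appendix A do not repeat it. The sentence in Section 2.1 is the only description of this component in the document.

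This matters at classification. The Clinical Events Committee adjudicates pre-defined events (Section 6.4.2) and no core laboratory is used (Section 6.3). Two adjudicators who accept the same facts about a late major valve injury could reach opposite answers, one from Section 2.1 and the other from Section 7.1. The safety rate is to be compared descriptively with the IDE and Continued Access studies, so the set of events that count should be fixed before the comparison is made.

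**Working it through.** The protocol states no figure for valve injury and gives no derivation of the 500 subjects, so there is nothing to reproduce. The check is textual, followed by an illustration of scale.

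**Step 1. Timing by component.**

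| Component | Section 2.1 admits delayed events | Appendix D has a delayed category |
|---|---|---|
| Access complications | Yes | Yes |
| Device embolization | Yes | Yes |
| Vessel stenosis | Yes | Yes |
| Valvular injury | No, immediate dysfunction only | Yes |

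**Step 2. Hypothetical related valve injuries under the two rules.**

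| Case | Section 2.1 read literally | Section 7.1 with Appendix A |
|---|---|---|
| Immediate dysfunction, major consequence | Counts | Counts |
| Immediate dysfunction first detected after 24 hours, major consequence | Counts | Counts |
| Dysfunction arising later, major consequence (for example open valve surgery) | Does not count | Counts |
| Late regurgitation, no major consequence | Does not count | Does not count |

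The rules differ only in the third case.

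**Step 3. Size per subject.** Inputs are 500 subjects (Sections 2 and 13), an expected major complication rate of 4.0 to 10.0% (Section 7.1) and an exact binomial 95% interval (Section 7.1). With x events among n subjects the rate is x/n, so one uncounted subject changes it by 1/500 = 0.2 percentage points. Section 7.4 excludes some subjects from the analysis, so n may be below 500 and the step slightly larger.

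**Step 4. Illustration.** The number k of late major valve injuries, in subjects with no other counted event, is an assumption. The protocol gives no such rate. The rate is (x + k)/500.

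| k | From 20/500 (95% CI) | From 50/500 (95% CI) |
|---|---|---|
| 0 | 4.0% (2.46 to 6.11) | 10.0% (7.51 to 12.97) |
| 1 | 4.2% (2.62 to 6.35) | 10.2% (7.69 to 13.19) |
| 5 | 5.0% (3.26 to 7.29) | 11.0% (8.39 to 14.08) |
| 10 | 6.0% (4.08 to 8.45) | 12.0% (9.28 to 15.18) |

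The last row is an extreme. Ten late major valve injuries would be 10/20 = half of all major complications expected at the low end of the range.

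**The case against.** A reader might infer that late valve damage is left out of the endpoint and that the safety rate is therefore understated. The documents do not support that, for four reasons.

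- Section 2.1 says its categories are broad and that valvular injury *includes* such damage. That is not the wording of an exhaustive definition.
- Section 7.1, which governs the calculation, refers to Appendix A and has no limit on onset. Under it a late major valve injury counts.
- Only major events enter the composite. New regurgitation at a follow-up echocardiogram with none of the Appendix A consequences stays outside it whatever its timing. If judged related, it is a minor complication, summarised under Section 7.5.
- The delayed box on the form may record late detection of an immediate injury, and the form also serves non-major events. Its presence does not show that late-onset injury was meant for the primary composite.

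All four stand, and they rule out the stronger claim. They do not remove the inconsistency. The word *includes* introduces the other descriptions in Section 2.1 as well, and those name delayed events expressly. Appendix A, to which Section 2.1 defers, is silent on valves. It is also fair that the study has no formal hypothesis, so no decision threshold moves. The estimate and its comparison with the earlier studies still depend on which events are counted.

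**Conclusion.** The concern holds as an inconsistency in the definition of a primary endpoint. Section 2.1, read literally, excludes late-onset major valve injury; Section 7.1 with Appendix A includes it; and the protocol does not say which prevails. It cannot be concluded from the protocol that the reported rate will be biased. If Section 2.1 is followed, the error can only lower the rate, by 0.2 percentage points for each such subject at n = 500.

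This rests on two assumptions: that the subject has no other counted event, and that the injury is judged related and meets an Appendix A consequence. The number of such injuries is unknown and probably small. The point merits correction because the component belongs to the primary endpoint and the repair is easy.

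**What to change.** In Section 2.1, delete *immediate* and describe valvular injury with the timing used for the other three components: during the procedure, after it, or delayed beyond 24 hours, through the six-month visit. Keep it subject to the Appendix A criterion for a major event. In Section 7.1 and Appendix A, state that a major device- or procedure-related valve injury counts whatever its onset within the window. Changing Section 2.1 alone would leave Appendix A silent on valves.

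The cost is a few phrases. The valve block of the adverse event form and the scheduled echocardiograms already collect the data, and no added testing is needed. The reported safety rate may be slightly less favourable.

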7.2 Primary Effectiveness Endpoint

The primary effectiveness endpoint is the rate of effective closure of the PDA among subjects with a successful device implant as assessed by the presence of either a Grade 0 or Grade 1 shunt (see **Appendix A** for definition) at the 6 month follow-up visit by transthoracic echocardiography.

The proportions of subjects who have effective closure of the PDA at follow-up will be calculated along with the 95% confidence interval. The numerator for the event rate is the number of subjects who have effective closure of the PDA at follow-up. The denominator is the number of subjects in the analysis population (As detailed in Section 7.4). The primary effectiveness endpoint will be compared with the rate reported in the ADO II AS and Continued Access Protocol studies.

Among subjects successfully implanted with any device, the PDA occlusion rate is estimated to be approximately 99%.

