7.5 Other Endpoints

The following endpoints will be summarized using descriptive statistics.

a. **Implant success:** The frequency and percentage of implant success (defined in Section 7.4) will be reported. This analysis will include all subjects entered in the PDA module.

- b. **PDA shunt status at follow-up visit**: The frequency and percentage of PDA shunt status at the 6 month follow-up visit, as assessed by the TEE, will be reported. Shunt sizes categories are: Grade 0/1, 2, and Grade 3/4. This analysis will include subjects who achieve a successful implant.
- c. **Obstruction measurements at follow-up visit**: The frequency and percentage of significant obstruction of the left pulmonary artery and the frequency and percentage of significant aortic obstruction (defined in Section 7.3) at the 6 month follow-up visit will be reported. Both analyses will include subjects who achieve a successful implant.
- d. **Major and Minor Complications**: The frequency and percentage of major and minor complications (refer to **Appendix A** for definition) from the time of the implant procedure will be reported.
- e. **Death**: The frequency and percentage of death will be reported.
- f. **Additional data**: Demographics and baseline characteristics, procedure information, left ventricular function and dimensions, pulmonic and tricuspid regurgitation, adverse events, subjects lost to follow-up will also be summarized.

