APPENDIX E: SCHEDULEOF ASSESSMENTS

	Pre- Catheterizatio	Device Implan	Follow up within 48 hours	Follow up at 30 ± 7 days	Follow up at 6 ± 1months
Domographia Data		шран	within 40110015	30 ± 7 uays	
Demographic Data	Х				
Physical Exam Data	Х		Х	Х	Х
Medical History					
Data	Х				
Procedure Data		Х			
Device Data		Х			
Transthoracic					
Echocardiogra					
m Data	Х	X *	Х	Х	Х
Adverse Event Data		Х	Х	Х	Х
Death Data		Х	Х	Х	Х
	* optional Intra-procedure Transthoracic Echocardiogram				

APPENDIXF

PROTOCOL DEVIATION REPORTING FORM

Report Date:	Title:	
Sponsor:	Principal Investigator:	
Date of Deviation/ Violation:	Subject Identifier: (if available)	

Reporting Deviations to IRB

*Sites must report violations that affect the safety and welfare of the subject to be submitted within 10 working days from the date the Investigator becomes aware of the event.

- Minor Deviations that do not affect the safety and welfare of the subject may be submitted at the time of continuing review. Please note that the sponsor's requirement may differ from IRB's reporting requirements; contact the sponsor and your institutional IRB to confirm if you have any questions regarding their policy.
- FDA 21 CFR 56.108(a)(4) and ICH 3.3.7 state that planned protocol deviations require prior approval of the IRB except when necessary to eliminate apparent immediate hazards to human subjects. Please submit this form to the CCISC as soon as possible after receiving sponsor approval for the planned deviation and prior to the deviation occurring.

Protocol Deviation/Violation Assessment		
Did the protocol deviation/violation affect the safe of the subject?	Yes* No	
Has the Sponsor been notified of this event?	Yes No	
Will the subject continue his/her participation in	Yes No	
Was the deviation planned or unplanned?	Planned**	Unplanned
(**please provide prior approval of Sponsor)		
Protocol Deviation/Violation Description and	Reason	

Please provide a description of the deviation/violation:

Please explain the reason for the	deviation/violation:	
-----------------------------------	----------------------	--

Corrective Action

Please describe what action(s) you have taken to prevent recurrence of this deviation/violation in the future:

Principal Investigator Signature:

Date:

Protocol Deviation Tracking Log

Tool:	Protocol Deviation Tracking Log				
Purpose:	To record all protocol deviations that occur at a study site				

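### Sections 2.1 and 7.2 define the primary effectiveness endpoint differently, so the same subject can be effective under one and not under the other, in either direction

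*Protocol*

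**What the plan says.** Section 2.1 of the protocol sets the effectiveness endpoint as the rate of effective closure within six months. It then gives four rules.

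- Where more than one attempt or device was needed in the procedure, the case is effective with "Grade 0 or Grade 1 shunt, as defined below, at follow-up (within six months) by transthoracic echocardiography (TTE").
- The same sentence adds a second route: "or if a second procedure is not required following the initial attempt". No shunt grade is attached to it.
- After embolization or adjacent vessel stenosis with retrieval, the condition is "replacement during the same procedure with less than Grade 1 shunt during follow-up, it is still considered effective".
- The one explicit failure rule concerns a later adverse event that "requires a second procedure for treatment that results in greater than Grade 1 shunt, then the procedure is considered not effective".

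The first sentence of section 7.2 defines the endpoint among successful implants as a Grade 0 or 1 shunt "at the 6 month follow-up visit by transthoracic echocardiography". Its counting rule is looser: "The numerator for the event rate is the number of subjects who have effective closure of the PDA at follow-up". It mentions no second procedure and no special threshold after replacement.

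Appendix E schedules transthoracic echo (TTE) within 48 hours, at a visit headed "Follow up at 30 ± 7 days", and at 6 ± 1 months. Section 7.5b separately reports "The frequency and percentage of PDA shunt status at the 6 month follow-up visit". Appendix A, to which 7.2 refers, defines the shunt grades but not effective closure.

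**The concern.** These are two definitions of one primary endpoint, and no text ranks them. An analyst who follows 2.1 and an analyst who follows the first sentence of 7.2 can classify the same subject differently. One route in 2.1 credits an untreated shunt of Grade 2 or more as effective closure. The report could then list a subject as a primary success and, in the 7.5b table, as Grade 2 or Grade 3/4.

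Section 7.6 says there is no formal hypothesis, so the estimated rate and its interval are the whole primary effectiveness result. They are to be set beside the earlier studies of the device. With about 1% failures expected, a handful of reclassified subjects is a large share of all failures.

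**Working it through.** **Step 1: classify example subjects under each section, read literally.**

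| Subject | Section 2.1 | Section 7.2, first sentence |
|---|---|---|
| A. Single device; Grade 1 at 30 days, Grade 2 at the six-month TTE | Can be effective (the early echo falls inside six months) | Not effective |
| B. Two devices in one procedure; Grade 2 at the six-month TTE; no second procedure | Effective (alternative route) | Not effective |
| C. Single device; first Grade 0 or 1 echo between six and seven months | Outside the six-month limit | Effective (inside the ± 1 month window) |
| D. Device retrieved and replaced in the same procedure; Grade 1 at the six-month TTE | Unclear: the replacement clause asks for below Grade 1, while the preceding sentence accepts Grade 0 or 1 | Effective |
| E. Later adverse event led to a second procedure that left Grade 2; Grade 1 by the six-month TTE | Not effective | Effective |

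In A and B, 2.1 is the more lenient section. In C and E it is the stricter one, and in D it may be. The disagreement has no fixed direction. Route B exists only for multi-attempt or multi-device cases; the difference in time point can touch any subject.

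**Step 2: illustrate the size.** The protocol gives no sample-size or precision figure for this endpoint to reproduce.

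Inputs:
- Expected occlusion rate about 99% (section 7.2).
- Initial cohort of 500 (sections 2 and 13). The number analysed is not stated, so 500 is an assumption; 400 is shown as an assumed lower case.
- Exact binomial (Clopper-Pearson) 95% limits. Section 7.1 names this method for safety; 7.2 names none, so its use here is also an assumption.

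Formulas: rate = x/n; lower limit = 2.5% quantile of Beta(x, n − x + 1); upper limit = 97.5% quantile of Beta(x + 1, n − x). When x = n the lower limit is 0.025^(1/n) and the upper limit is 1.

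Expected failures: 500 × (1 − 0.99) = 5, and 400 × 0.01 = 4. Each reclassified subject moves the rate by 1/500 = 0.2 points, or by 1/400 = 0.25 points.

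| Scenario | x/n | Rate | 95% limits |
|---|---|---|---|
| Base, n = 500 | 495/500 | 99.0% | 97.68 to 99.67 |
| 1 failure becomes a success | 496/500 | 99.2% | 97.96 to 99.78 |
| 3 failures become successes | 498/500 | 99.6% | 98.56 to 99.95 |
| All 5 failures become successes | 500/500 | 100% | 99.26 to 100 |
| 5 successes become failures | 490/500 | 98.0% | 96.35 to 99.04 |
| Base, n = 400 | 396/400 | 99.0% | 97.46 to 99.73 |
| All 4 failures become successes | 400/400 | 100% | 99.08 to 100 |

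The number reclassified is assumed in every row. The protocol gives no basis for predicting it.

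**Step 3: subjects without a six-month TTE.** Section 7.4 removes subjects with no follow-up visit and those lost to follow-up, and section 6 requires two missed visits before a subject counts as lost. A subject seen at 30 days who misses only the six-month visit can therefore stay in the denominator. An early Grade 0 or 1 echo can make that subject effective under 2.1, while 7.2 offers no six-month reading. How many there will be is unknown, so this effect is not quantified.

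**The case against.** The best defence is that 7.2 is the operative definition. It sits in the statistical section, names visit, method and threshold, and matches the visit used in 7.5b. An analyst would most naturally follow it and read its counting sentence as meaning the six-month visit. That is plausible, but the protocol does not say so, and 2.1 is the section that formally sets the endpoint.

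A second defence is that 2.1 meant to require both conditions and that its alternative is a slip. That may be so; the text still offers an alternative. A third is that 2.1 intends the six-month limit to include the visit window of section 1.2, which would remove case C. It would not remove A, B or E.

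The analysis plan is not shown. How to handle a missing six-month TTE can properly be left to it and is not part of this point. Two conflicting definitions within the protocol are a different matter, because a later plan could follow either.

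Three stronger readings are tempting and are not supported.

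- A reader might infer that 2.1 can only inflate the rate, so that 99% to 100% is the full range. Cases C and E, and possibly D, run the other way, and subjects without a six-month TTE add an unknown amount.
- A reader might infer that any open duct counts as closed under 2.1 so long as nobody reintervenes. That route is written only for multi-attempt or multi-device cases.
- A reader might infer damage to a test. There is no hypothesis, margin or success criterion for this endpoint.

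**Conclusion.** The inconsistency is real and should be fixed. Sections 2.1 and 7.2 differ in time point, in the route to success without a shunt condition, in the threshold after same-procedure replacement, and in the rule on second procedures driven by adverse events. The replacement threshold is an ambiguity in wording rather than a stated reversal. The discordance can raise or lower the reported rate.

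The figures are illustrative and rest on the stated 99%, an assumed 500 analysed, and exact limits. On that basis each reclassified subject is worth 0.2 points, and crediting all 5 expected failures would move 99.0% (97.7 to 99.7) to 100% (99.3 to 100). The 99% is itself a loose anchor, because 7.2 gives it as an occlusion rate with any device. What is affected is the primary rate, its interval and the descriptive comparison with the earlier studies.

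**What to change.** Use one definition in 2.1 and in both sentences of 7.2: Grade 0 or Grade 1 shunt by TTE at the six-month (± 1 month) visit. To get there:

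1. Remove the 2.1 route that rests only on the absence of a second procedure, or make it conditional on Grade 0 or 1.
2. Align the replacement clause in 2.1 with the Grade 0 or 1 threshold.
3. State the rule on second procedures driven by adverse events identically in both sections, so that it does not survive in 2.1 alone.
4. Name the six-month visit in the counting sentence of 7.2.

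Handling of a missing six-month TTE may be left to the analysis plan.

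The cost is wording only. Appendix E already schedules the six-month TTE, and section 4.4 already asks for residual shunting to be recorded. The downside is that the reported effectiveness rate may be lower than under the more lenient parts of 2.1.

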7.4 Analysis Population

The analysis of the primary and secondary endpoints will include all subjects who achieve a successful implant, which is defined as leaving the catheterization lab with a device implanted in the PDA. If a subject has multiple devices attempted during the same procedure, but leaves procedure with at least one device within the PDA the procedure is considered successful. Subjects without an implanted device in the PDA will be excluded. Additionally, subjects who had no follow- up visits up to the six-months +/- one-month window, or lost to follow-up will be excluded.

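### Section 2.1 sets a Grade 0 threshold for retrieved-and-replaced devices, while the sentence before it and section 7.2 use Grade 0 or Grade 1

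*Protocol*

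**What the plan says.** The effectiveness paragraph of Protocol section 2.1 has four sentences.

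- The first names the endpoint: the rate of effective closure within six months.
- The second covers "If more than one attempt is required, or multiple devices are required during the same procedure" and counts these as effective at Grade 0 or Grade 1 on follow-up transthoracic echocardiography. It adds an alternative: the case is also effective if no second procedure proves necessary after the first attempt.
- The third covers embolization or adjacent vessel stenosis: "retrieval of the device and replacement during the same procedure with less than Grade 1 shunt during follow-up, it is still considered effective".
- The fourth gives the only express failure rule. It concerns an adverse event that "requires a second procedure for treatment that results in greater than Grade 1 shunt, then the procedure is considered not effective".

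The scale that follows runs Grade 0 (none), then "Grade 1—trivial (narrow jet adjacent to the device via the PDA", then Grade 2 and Grade 3/4. There is nothing between 0 and 1.

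Protocol section 7.2 restates the endpoint for all successfully implanted subjects, "as assessed by the presence of either a Grade 0 or Grade 1 shunt", with no exception for replaced devices. Section 7.5, item b, reports Grade 0 and Grade 1 as one category. Section 7.4 keeps these infants in the analysis: "If a subject has multiple devices attempted during the same procedure, but leaves procedure with at least one device within the PDA" is a successful implant.

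**The concern.** A responder threshold for a primary endpoint should give each subject one status. Here the threshold tightens from Grade 0 or 1 to Grade 0 alone for the infants whose procedure was complicated by embolization or stenosis, and no reason is given. An analyst who follows the specific sentence in 2.1 and an analyst who follows 7.2 would classify the same Grade 1 infant differently.

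The situation is one the protocol expects. Appendix A lists intra-operative embolization with transcatheter retrieval among its minor complications, and the adverse event form in Appendix D has entries for retrieval followed by closure with another device. The stricter reading can only lower the estimated rate. Section 7.6 states that there is no formal hypothesis, so the estimate itself is the result.

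**Working it through.** **1. What the scale allows.** Grades are whole categories, with Grade 0 as none and Grade 1 as trivial. Less than Grade 1 is therefore Grade 0 only.

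**2. Whether the second and third sentences of 2.1 cover the same infants.** A device retrieved and replaced by another in the same procedure is a multiple-device case. If the same device is put back, which Appendix D also lists for vessel stenosis, the overlap comes through the repeat-attempt wording. In both situations the second sentence applies as well as the third.

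**3. One infant put through every rule.** A device embolizes in the laboratory, is retrieved and replaced in the same procedure, no second procedure follows, and Grade 1 is seen at six months.

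| Rule | Condition | Result at Grade 1 |
|---|---|---|
| 2.1, second sentence, grade limb | Grade 0 or 1 | effective |
| 2.1, second sentence, alternative limb | no second procedure needed | effective |
| 2.1, third sentence | below Grade 1 | condition not met |
| 2.1, fourth sentence | second procedure and above Grade 1 | failure rule not triggered |
| 7.2 | Grade 0 or 1 | effective |
| 7.5, item b | Grade 0/1 pooled | counted with Grade 0 |

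Only the third sentence is out of line.

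**4. The same infant at Grade 2.** The grade limb, the third sentence and 7.2 are not met. The alternative limb is met, because no second procedure was needed. Correcting the third sentence alone would therefore leave 2.1 and 7.2 in disagreement for Grade 2 and above.

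**5. Scale.** The protocol gives no figure on this point to reproduce. Two inputs come from it: 500 subjects (sections 2 and 13) and an occlusion rate of about 99% (section 7.2).

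- Effect of one infant: 1/500 = 0.2 percentage points.
- Expected non-closures at 99%: 500 × 0.01 = 5, leaving 495.

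The share of infants with retrieval and replacement, and the share of those at Grade 1, are not in the protocol. The ranges here are assumptions: 1% to 5% and 5% to 30%.

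- Low: 500 × 0.01 × 0.05 = 0.25 infants.
- High: 500 × 0.05 × 0.30 = 7.5 infants.

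Exact (Clopper-Pearson) 95% intervals, with k infants moved from effective to not effective:

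| k | Effective | Rate | 95% interval |
|---|---|---|---|
| 0 | 495/500 | 99.0% | 97.68% to 99.67% |
| 1 | 494/500 | 98.8% | 97.41% to 99.56% |
| 3 | 492/500 | 98.4% | 96.87% to 99.31% |
| 7 | 488/500 | 97.6% | 95.85% to 98.75% |

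The 500 is an upper bound on the denominator, because 7.4 excludes infants without an implanted device and those without follow-up. With fewer analysed, each infant weighs slightly more than 0.2 points.

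**The case against.** The strongest reply is that the third sentence states a sufficient condition for success and nothing more. It does not say that Grade 1 fails, and the only express failure rule in 2.1 needs a shunt above Grade 1. A reader might infer that the protocol formally classes one infant as both a success and a failure. The text does not go that far: the exclusion is by implication. The implication is still a fair one, because a specific condition after a general one does no work if Grade 1 passes anyway.

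It can also be said that this is a drafting slip for Grade 1 or less. The fourth sentence, 7.2 and 7.5 all point that way, and an analyst working from 7.2 alone would meet no ambiguity about the grade. That is probably right, and it limits the practical risk. It is a reason to correct the phrase. A statistical analysis plan could choose one threshold, but the protocol's other sentence would still contradict it.

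Two further inferences are tempting and should be resisted.

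- That the stricter wording breaks comparability with the IDE and Continued Access studies: the protocol does not give the responder definitions used there, so this cannot be judged.
- That the reclassified infants could equal or exceed the roughly five expected non-closures: this needs assumed rates near the top of their ranges together. The 99% is also quoted for any device and is not tied expressly to this responder definition.

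**Conclusion.** The threshold in the third sentence of the effectiveness definition is wrong as written. It conflicts with the second sentence of the same paragraph and with 7.2, and it does not fit the fourth sentence or 7.5. The conflict concerns one group, infants with a device retrieved and replaced in the same procedure, and one result, Grade 1.

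The effect is probably small. What can be stated from the protocol is 0.2 percentage points per infant at 500 subjects, against an expected rate of about 99%. How many infants are involved rests wholly on assumed rates, and at the low end of those rates it may be none. No sample size, error rate or pass/fail decision is affected. The point is still worth correcting, because it sits in a primary endpoint definition and leaves a choice that could be made after the data are seen.

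**What to change.** In the third sentence of the effectiveness definition in 2.1, replace the less-than-Grade-1 condition with Grade 0 or Grade 1 shunt at follow-up, matching 7.2.

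That edit alone does not give one cut-off for all subjects. The alternative limb of the second sentence, which accepts a case when no second procedure is needed whatever the shunt grade, must also be reconciled with 7.2. It can be removed, or made an additional requirement alongside the grade, so that Grade 2 or higher is not counted as effective.

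If a stricter threshold for replaced devices was intended, the protocol should say so, give the reason, and carry the exception into 7.2.

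The cost is two wording changes in one paragraph. No new data are needed, since section 4.4 already asks for the degree of residual shunting at follow-up.
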